### 5.5.4 Specifications for Concomitant Therapy (e.g., Medication)

Based on interventional guidelines in China and at abroad, dual antiplatelet

therapy is recommended to minimize the risk of thrombosis. The initial oral loading dose for all patients without contraindications to aspirin is 100~300 mg, which will be maintained for a long time at 100 mg/d. A P2Y12 receptor antagonist is added in addition to aspirin and maintained for at least 12 months, unless there are contraindications (e.g. higher risk of hemorrhage). Options include:

- Ticagrelor: Loading dose of 180 mg, maintenance dose of 90 mg, bid;
- Clopidogrel: loading dose of 300~600 mg, maintenance dose of 75mg, qd.

Investigators can make decisions on the use of dual-antiplatelet drugs in patients according to clinical conditions, including whether pre-procedure loading dose is required.

Low-density lipoprotein control with an optimal lipid-lowering regimen is recommended, with an LDL target of  $\leq 1.8$  mmol/L ( $\leq 70$  mg/dL), moderate-intensity statins recommended, and a combination with non-statins recommended if the OPC is not reached.

## 5.6 Measures to Control Bias

- (1) In terms of trial design, the randomized, parallel-controlled clinical trial design is used, which can make the distribution of clinical trial influencing factors between the test group and control group tend to be balanced, reducing the selection bias and implementation bias. The objective judgment endpoints are adopted to avoid measurement bias.
- (2) In terms of trial implementation, the investigators in various sites use the same methods, follow the same standard operating procedures (SOPs), and receive uniform trainings before the trial to reduce observer bias. Subjects will be screened in strict accordance with the inclusion and exclusion criteria in the clinical trial protocol to reduce selection bias. The clinical research associate (CRA) appointed by the Sponsor shall regularly conduct monitoring on the study sites, making sure that all contents in the trial protocol are strictly followed. The raw materials are inspected to ensure consistent contents with the Case Report Form (CRF).
- (3) In terms of independent imaging evaluation, the addition of independent imaging analysis is not excluded in this trial.
- (4) To minimize bias, blinded data review may be considered. For possible confounding bias, appropriate control may be considered in the data analysis phase.

## 6. Statistical Considerations

### 6.1 Estimation of Sample Size

### 6.1.1 Overall Sample Size

After literature review, according to the results of relevant study literature and clinical experience of the scoring balloon catheter in the treatment of coronary artery disease, assuming that the SINOMED Coronary Scoring Balloon Catheter in the test group and Goodman NSE Coronary Dilatation Catheter in the control group can reach the equivalent level, then the device success rate is expected to reach 96% [10, 14-17]. Considering the influence of factors such as the procedure level of different investigators, the complexity of lesions, and the comorbidities and severity of illness of subjects, the sponsor, clinical experts, investigators and statistical experts jointly decide that the non-inferiority margin  $\delta$  is taken as -10%, the one-sided test  $\alpha$  is set to be 0.025, and the test power  $(1-\beta)$  is 0.8. The total sample number is calculated as 122 using the PASS software, with 61 each in test group and control group. In consideration of a 10% dropout rate, this study requires 136 subjects, 68 each in test group and control group. The formula for calculation of sample size is shown as follows:

$$n_T = n_C = \frac{(Z_{1-\alpha/2} + Z_{1-\beta})^2 [P_C(1 - P_C) + P_T(1 - P_T)]}{(|D| - \Delta)^2}$$

Note:  $n_T$  and  $n_C$  are the sample sizes of test group and control group, respectively, and  $Z_{1-\alpha/2}$  and  $Z_{1-\beta}$  are the quartiles of the standard normal distribution; when  $\alpha=0.025$ ,  $Z_{1-\alpha/2} = 1.96$ , and when  $\beta=0.2$ ,  $Z_{1-\beta}=0.842$ ;  $(Z_{1-\alpha/2}+Z_{1-\beta})^2=7.85$ ;  $P_T$  and  $P_C$  are the predictive incidences of events in test group and control group, respectively, and  $|D|$  is the absolute value of the expected rate difference between the two groups  $|D| = |P_T - P_C|$ , and  $\Delta$  is the non-inferiority margin, being negative.

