#### **5. Study Design**

##### **5.1 Overall Design and Its Determination Basis**

This clinical trial is a prospective, multicenter, randomized, parallel controlled, non-inferiority design.

Multicenter clinical trial: refers to the clinical study conducted in two (inclusive) or more medical device clinical trial institutions under the same clinical trial protocol.

Parallel controlled design: Based on the Guidance for the Design of Medical Device Clinical Trials, the controlled clinical trial is conducted using the marketed devices with recognized efficacy/safety. The Coronary Scoring Balloon Catheter is a class III medical device, and there are few similar products on the market. In order to evaluate the effectiveness and safety of Coronary Scoring Balloon Catheter, the NSE Coronary Dilatation Catheter (NMPA (I) 20163035067), which is similar in structure and operating principle, relatively widely used in clinical practice and has positive efficacy in China and abroad, is

selected as the control device after investigation.

**Randomization:** Randomization is the basic principle to be followed by parallel controlled clinical trials. Each subject in a clinical trial has the same opportunity (the ratio of cases in test group to control group is 1:1) to be assigned to test group or control group, without affection of subjective wishes of the investigator and/or subject, to ensure the subjects in test group and control group comparable in various known and unknown baseline variables that may affect the trial result.

**Blinding:** Due to the different inherent characteristics (appearance, marking, etc.) of the investigational medical device and the control device, the subjects and investigators cannot be blinded in the trial, so an open-label design is adopted.

**Non-inferiority test:** The non-inferiority test is selected to confirm the efficacy/safety of the investigational medical device, which if lower than that of the control device but the difference between them is less than the pre-set non-inferiority margin, the difference is clinically acceptable.

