### (3) Primary efficacy endpoint

The Primary efficacy endpoint of this study is the device success rate (lesion level), and the hypothesis test is as follows:

Null hypothesis:  $P_T - P_C \leq -10\%$

Alternative hypothesis:  $P_T - P_C > -10\%$

Under  $\alpha=0.025$  (one-sided test) and  $\beta=0.2$ , the device success rate (lesion level) is compared between the test group and control group, and the difference between the two groups and the 95%CI of such difference are calculated to determine whether the non-inferiority margin is met based on the lower limit of CI. Non-inferiority is established if the lower limit of 95%CI is not lower than -10%. If

central effect is to be considered, CMH's chi-square test is used.

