### **6.4.3 Significance Level and Power of Clinical Study**

In this trial, for the primary endpoint, the significance level of statistical test is 0.025% one-sided, and the power of test is taken as 80%. For other indicators, the significance level of statistical test is taken as 0.05 two-sided.

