### **6.4.4 Expected Drop-out Rate**

In determining the sample size, the highest possible drop-out rate during the study is expected to be 10%, including all conditions that make the subjects ultimately excluded from the primary analysis, often referring to major deviation of trial protocol (affecting the primary efficacy evaluation and/or safety evaluation) adjudicated by the PIs.

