1.5. Sample size

Based on literature review, clinical experience, and results from studies evaluating scoring balloon catheters for coronary artery disease, it is hypothesised that the study group's Sino scoring balloon dilation catheter will demonstrate comparable efficacy to the control group's Goodman coronary NSE balloon catheter, with an anticipated device success rate of 96%. Considering factors such as operator skill variation, lesion complexity, and subject comorbidities and disease severity, the sponsor, clinical experts, investigators, and statisticians jointly determined a non-inferiority margin Δ of -10%, a one-sided test α of 0.025, and a test power (1- β) of 0.8. PASS software calculations yielded a total sample size of 122 subjects, with 61 subjects in each group. Accounting for a 10% dropout rate, the trial requires 136 subjects, distributed as 68 in each group. The sample size calculation formula is as follows:

$$n_T = n_C = \frac{\left(Z_{1-\frac{\alpha}{2}} + Z_{1-\beta}\right)^2 [P_C(1 - P_C) + P_T(1 - P_T)]}{(|D| - \Delta)^2}$$

Where n_T and n_C denote the sample sizes for the treatment and control groups respectively, $Z_{1-\frac{\alpha}{2}}$ and $Z_{1-\beta}$ represent the quantiles of the standard normal distribution, P_T and P_C denote the expected event rates for the treatment and control groups respectively, $|D| = |P_T - P_C|$ denotes the absolute difference in expected rates between the two groups, and Δ denotes the non-inferiority margin, taken as a negative value.

This trial will be conducted concurrently across multiple clinical trial sites. In principle, enrolment numbers will be distributed as evenly as possible among centres to ensure adequate representativeness. However, considering feasibility and enrolment progress, adjustments to enrolment quotas for participating sites will be made based on actual circumstances, striving to maintain balanced enrolment scales across centres. The final enrolment size for any single centre shall not exceed 50% of the total number of cases.

2. Evaluation Criteria

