
4. Handling of missing data

For patients in the FAS who did not have an observation for the primary efficacy endpoint, worst observation carried forward was applied. For target lesions where device success could not be determined, imputation was performed as 'device failure'. No imputation was performed for secondary endpoints or efficacy endpoint in the PPS. Missing safety data were not imputed.

5. Statistical Analysis Methods

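### 80% power and one-sided 0.025 are not achieved together at 61 or 68 per arm with any of the confidence intervals checked, and the 10% dropout allowance does not protect the FAS analysis

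*Protocol*

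**What the plan says.** Protocol 6.1.1 assumes equal performance in the two arms: "then the device success rate is expected to reach 96" per cent. SAP 1.5 sets "a one-sided test α of 0.025, and a test power (1- β) of 0.8", with a margin of -10 percentage points. Allocation is equal (Protocol 5.1: "the ratio of cases in test group to control group is 1:1"). The result in Protocol 6.1.1 is: "The total sample number is calculated as 122 using the PASS software, with 61 each in test group and control group". The 10% dropout allowance brings this to 136, or 68 per arm.

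The decision rule in Protocol 6.4.2 (3) is: "Non-inferiority is established if the lower limit of 95%CI is not lower than -10" per cent. The interval method is not given in the protocol, and Note 1 to SAP Table 19 has only an XX placeholder for it.

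Protocol 6.4.4 describes the 10% as "including all conditions that make the subjects ultimately excluded from the primary analysis". For the FAS, SAP section 4 says: "For target lesions where device success could not be determined, imputation was performed as" device failure. Nothing is imputed in the PPS.

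Protocol 6.4.3 prints the level for the primary endpoint differently: "the significance level of statistical test is 0.025% one-sided, and the power of test is taken as 80" per cent.

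**The concern.** The formula is a large-sample approximation with unpooled variances. At 96% success and 61 lesions per arm, only 61 × 0.04 = 2.4 failures per arm are expected. With counts that small, power and type I error depend strongly on which interval is used, and the plan names none. If the interval holds the error rate, a truly equivalent device is more likely to miss non-inferiority than the stated 20%. If it keeps the power, the false-positive rate exceeds the stated 2.5%.

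The dropout allowance raises a separate issue. Dividing by 0.90 protects power only if the lost lesions leave the analysis. Counting a lesion as a failure keeps it in the denominator and lowers the success rate, which costs more power than losing it.

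**Working it through.** **Inputs.** Success is 0.96 in both arms, margin 0.10, z-values 1.96 and 0.842, dropout 10% (Protocol 6.1.1, SAP 1.5). The rule is the lower limit of a two-sided 95% interval (Protocol 6.4.2). Assumption, because the documents give no lesion count: one lesion per subject.

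**The plan's own figure.** n = (1.96 + 0.842)² × 2 × 0.96 × 0.04 / 0.10² = 7.85 × 7.68 = 60.3, rounded up to 61. Then 61 / 0.90 = 67.8, rounded up to 68. Both reproduce.

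**Exact power and error.** For each interval, take every pair of success counts whose lower limit meets -10% and sum the product of the two binomial probabilities. Power is evaluated at 96% vs 96%, and one-sided error at 86% (test) vs 96% (control).

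| Interval or test | Power, n=61 | Error, n=61 | Power, n=68 | Error, n=68 |
|---|---|---|---|---|
| Wald | 81.9% | 4.5% | 85.3% | 4.2% |
| Agresti-Caffo | 74.2% | 2.9% | 78.9% | 3.0% |
| Wald, continuity-corrected | 66.6% | 1.8% | 70.6% | 1.8% |
| Newcombe | 66.3% | 2.5% | 69.8% | 2.2% |
| Miettinen-Nurminen | 64.6% | 1.9% | 69.8% | 2.2% |
| Exact unconditional | 59.0% | 1.8% | 63.5% | 1.6% |

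No row has both at least 80% power and at most 2.5% error.

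**Why they differ.** Take 61 per arm with 3 test failures and 2 control failures. The difference is 58/61 - 59/61 = -0.0164.
- Wald: the standard error is √[(3×58 + 2×59)/61³] = √(292/226,981) = 0.0359. The lower limit is -0.0164 - 1.96 × 0.0359 = -8.7%, a pass.
- Newcombe: the Wilson lower limit for the test arm is 0.8651 and the Wilson upper limit for the control arm is 0.9910. The lower limit is -0.0164 - √[(0.9508 - 0.8651)² + (0.9910 - 0.9672)²] = -0.0164 - 0.0890 = -10.5%, a fail.

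**Failure imputation in the FAS.** If a share m of lesions in each arm is undeterminable, unrelated to outcome, and counted as failure, the success rate becomes 0.96 × (1 - m) with n still 68.

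| m | Success rate | Newcombe or Miettinen-Nurminen | Wald |
|---|---|---|---|
| 0% | 96.0% | 69.8% | 85.3% |
| 2% | 94.1% | 59.6% | 72.7% |
| 5% | 91.2% | 48.7% | 56.3% |
| 10% (worst case) | 86.4% | 37.5% | 40.8% |

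If 10% were excluded instead, 61 lesions at 96% would remain, with 65-66% power (Newcombe or Miettinen-Nurminen) or 82% (Wald).

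**Extra lesions.** With all lesions independent and none missing, Newcombe gives 77.7% at 75 lesions per arm and 79.9% at 82. Depending on the method (Newcombe, Farrington-Manning or Miettinen-Nurminen), about 80 to 86 lesions per arm are needed for 80%.

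**The case against.** **The sample size is calculated correctly.** This stands. The formula is a standard one and gives 61 and 68. The limitation is the approximation, not the arithmetic.

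**The shortfall depends on a method not yet chosen.** This also stands. A reader might infer that 80% power is simply not reached, but with Wald, which matches the printed formula, it is. The excess is then in type I error. Agresti-Caffo falls between the two. "Holding" 2.5% is itself approximate: over other control rates, the maximum error reaches 2.7-2.8% for Newcombe and 2.6-2.7% for Miettinen-Nurminen.

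**The unit is the lesion, and a subject may have two.** Second lesions would raise power, but within-subject correlation would reduce the gain. The documents give neither the number of lesions nor the correlation, so 65-70% is a one-lesion scenario.

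**The planned 10% are not imputed failures.** A reader might infer that the plan's own dropouts bring power to 38-41%. The documents do not support this. Protocol 6.4.4 describes subjects excluded from the primary analysis, often for major deviations. Untreated subjects are outside the FAS, subjects with deviations stay in it with their observed outcome, and the PPS is not imputed. The endpoint is read at the procedure, so later withdrawal does not remove it. Only a treated lesion whose success cannot be determined becomes a failure. That can happen, for example with a film unreadable by the core laboratory that supplies residual stenosis (SAP Table 21, Note 2), but the plan does not predict it for 10%.

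**The 0.025% is a misprint.** Read literally it would need (3.481 + 0.842)² × 7.68 = 143.5, so 144 per arm. Protocol 6.1.1 and 6.4.2 and SAP 1.5 all give 0.025, and the rule uses a 95% interval, so that reading is not credible.

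**Conclusion.** The point holds in conditional form. At 61 or 68 lesions per arm, none of the methods checked gives both the stated 80% power and the stated one-sided 2.5% error. With Wald, the error is 4.2-4.5%. With Newcombe or Miettinen-Nurminen, the chance of missing non-inferiority for a truly equivalent device is about 30-35% instead of 20%. Because the interval is unnamed, the plan does not show which stated property fails.

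Separately, the 10% allowance covers exclusions and does not protect FAS power against failure imputation. A 2% share already takes Wald below 80% and Newcombe or Miettinen-Nurminen to about 60%.

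These figures assume 96% success in both arms before imputation, one lesion per subject, and an equal imputed share in each arm. Low power does not bias the estimated difference. The false-positive risk arises only if an interval such as Wald is chosen.

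**What to change.** Keep 136 subjects and make these text changes before the SAP is finalised, which Protocol 6.4.7 requires before database lock:

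- **SAP 5.4.1 and Table 19, Note 1:** name the interval, choosing one that holds about 2.5% at these rates, such as Newcombe or Miettinen-Nurminen.
- **Protocol 6.1.1 and SAP 1.5:** restate power for that method as about 65% at 61 and 70% at 68 evaluable lesions per arm, assuming 96% in both arms and one lesion per subject. Add that two-lesion subjects would raise power by an amount that depends on within-subject correlation.
- **Protocol 6.4.4 and SAP section 4:** state that the 10% allowance covers exclusions only. Give FAS power at 2% and 5% imputed failures, with 10% labelled as a worst case.
- **Protocol 6.4.3:** correct 0.025% to 0.025.

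No patients are added. The cost is a less favourable stated power.

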### 6.1.2 Allocation of Sample Size

The inclusion/exclusion criteria for the selected subjects are strictly restricted in this trial protocol, and all selected 136 subjects are diagnosed with coronary artery stenosis (including in situ or restenotic lesions). The subjects screened are randomized at 1:1 to receive the investigational medical device or the control device for treatment, and the device success rate is set as the primary endpoint.

### 6.1.3 Minimum and Maximum Number of Subjects in Each Site and Justification

This trial will be carried out at the same time in multiple study sites. In principle, the number of subjects enrolled in each site will be distributed as evenly as possible to ensure adequate site representation. However, considering the feasibility and progress of the selection, the number of subjects enrolled in each participating site will be adjusted according to the actual situation, so as to ensure that the enrollment scale at each site is relatively balanced, and that the final enrollment scale for a specific site should not exceed 50% of the total number of

cases.

## 6.2 Analysis Data Sets

Statistical analysis will be carried out on the basis of the following analysis populations. The analysis populations will be clearly defined before the start of statistical analysis. And the analysis populations in this study include:

- (1) Full Analysis Set (FAS): the set of subjects determined following the intent-to-treat (ITT) principle refers to the data set constituted by all subjects who participate in the randomized study and receive the investigational product. The worst observation carried forward (WOCF) is used for imputation of the patients in whom the Primary efficacy endpoint is unable to be observed.
- (2) Per-Protocol Set (PPS): refers to the subgroups of treatment population where the study has been completed with the major protocol violations excluded (which means that the subjects violate the inclusion criteria or exclusion criteria, etc.).
- (3) Safety set (SS): refers to the subject dataset using investigational medical devices and having recorded safety endpoints.

The efficacy analysis will be performed based on the FAS and PPS. All baseline demographic data analysis will be performed on the FAS while the safety evaluation will be on the SS.

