## Protocol Abstract

Study Title	A Prospective, Multicenter, Randomized Controlled Study to Evaluate the Safety and Effectiveness of Coronary Scoring Balloon Catheter for the Treatment of Coronary Artery Disease
Study Objective	To evaluate the safety and effectiveness of Coronary Scoring Balloon Catheter manufactured by Sino Medical Sciences Technology Inc. in the treatment of coronary artery stenosis
Test Devices	
 
● Investigational Medical Device: Product Name: Coronary Scoring Balloon Catheter Manufacturer: Sino Medical Sciences Technology Inc.
 
● Control Device: Product Name: NSE Coronary Dilatation Catheter Manufacturer: Goodman Co., Ltd. Medical Device Registration Certificate No.: NMPA (I) 20163035067
 

Estimation of Sample Size	After literature review, according to the results of relevant literature and clinical experience of the scoring balloon catheter in the treatment of coronary artery disease, assuming that the SINOMED Coronary Scoring Balloon Catheter in the test group and Goodman NSE Coronary Dilatation Catheter in the control group can reach the equivalent level, and the device success rate (lesion level) is expected to reach 96%, with one-sided test $\alpha$ as 0.025, test power ( $1-\beta$ ) as 0.8 and non-inferiority margin $\delta$ as -10%, the number of cases to be included in each group is 61 as calculated by PASS software. In consideration of a 10% dropout rate, this study requires 136 subjects, 68 each in test group and control group.

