## **5.2 Subject Enrollment**

### **5.2.1 Inclusion Criteria**

- (1) Patients are at least 18 to 75 years of age, male or not pregnant female;
- (2) Patients with asymptomatic ischemic evidence, stable or unstable angina pectoris or old myocardial infarction;
- (3) In situ or restenotic lesion(s) in coronary arteries, including in-stent restenosis (ISR);
- (4) Target lesion(s) must have a diameter of 2.0 mm ~ 3.5 mm and a length of  $\leq 30$  mm;
- (5) Target lesion(s) must have a percent diameter stenosis of  $\geq 70\%$  or  $\geq 50\%$  with evidence of ischemia;
- (6) Patients have a planned intervention at no more than two lesions, in different target vessels;
- (7) Investigators believe that target lesion atherosclerotic plaques require the scoring balloon treatment, in which the balloon can be passed through by pre-dilation.
- (8) Able to understand the purpose of the trial, voluntarily participate and sign the ICF.

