2.2. Safety Evaluation

1) Target lesion failure composite endpoint (TLF) incidence

Any of the following events constituted a TLF:

- a. Cardiovascular death (including cases where the cause of death is uncertain but considered cardiovascular in origin);
- b. Target Vessel-Related Myocardial Infarction (TV-MI);
- c. Clinically-indicated target lesion revascularisation (CI-TLR).

Evaluation method: The observation period spans from the commencement of procedure until discharge. For each subject, the incidence rates of individual events and the composite event rate are calculated.

2) Incidence of the patient-oriented composite endpoint (PoCE)

Any occurrence of the following events constituted a PoCE:

- a. All-cause mortality;
- b. All myocardial infarctions;
- c. All recurrent revascularisation events, including target lesion revascularisation (TLR), target vessel non-target lesion revascularisation (TVR), and non-target vessel revascularisation.

Evaluation method: The observation period spans from the commencement of procedure until discharge. For each subject, the incidence rate of individual events and the composite event rate shall be separately calculated.

3) Incidence of Individual Adverse Events and Serious Adverse Events

Evaluation Method: The observation period spans from the commencement of procedure until discharge. Other potential adverse events include balloon rupture, vascular perforation, dissection, acute occlusion, vasospasm, thrombosis (including in-stent thrombosis), and arrhythmias requiring intervention. The incidence rate of each individual event shall be separately calculated.

4) Incidence of device deficiency

3. Analysis Data Set

Full Analysis Set (FAS): The population defined according to the intention-to-treat principle, comprising all subjects who were randomised and received the study product. For patients with missing primary efficacy endpoint data, worst observation carried forward (WOCF) was applied.

Per-protocol set (PPS): Subgroup of the completed trial population excluding major protocol deviations (e.g., subjects breaching inclusion or exclusion criteria).

Safety Set (SS): Refers to the dataset comprising subjects who used the investigational device and for whom safety endpoints were recorded.

Efficacy analyses will be conducted based on both the full analysis set and the per-protocol set. All baseline demographic analyses utilise data from the full analysis set, while safety evaluations employ the safety set.

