6.1. Subject distribution

Table 1 Case distribution across centres

Centre Code	Research Centre	Group	Number					Exclusion rate (%)	Completed
			Screening Failure	Screening Enrolment	Dropout Count	Dropout rate (%)	Dropout of exclusions		
01	Centre 1	Experimental Group							
		Control Group							
		Total							
02	Centre 2	Experimental group							
		Control group							
		Total							
03	Centre 3	Experimental group							
		Control group							
		Total							
.....									
	Total	Experimental group							
		Control group							
		Total							

Note 1: Number of completions = Number enrolled - Number of dropouts.

Note 2: Exclusion refers to subjects who completed the trial but were not included in the PPS set.

Table 2 Subject Grouping by Centre

Centre Name	FAS		Total	PPS		Total	SS		Total
	Experimental Group	Control Group		Experimental group	Control Group		Experimental group	Control group	
01									

Centre Name	FAS			PPS			SS		
	Experimental Group	Control Group	Total	Experimental group	Control Group	Total	Experimental group	Control group	Total
02									
03									
.....									
Total									

Table 3 Enrolled Cases and Safety/Efficacy Analysis Dataset

Item	Indicator	Experimental Group	Control Group	Total
Screening	Screening conducted			
	Screening Failure			
Randomisation status	Randomised allocation			
Trial completion status	Trial not completed			
	Completed trial			
Reasons for trial discontinuation	Subject declined to continue participation in the study for any reason			
	Withdrawal deemed necessary by the investigator for medical or safety reasons			
	Serious protocol deviation (as confirmed by the principal investigator)			
	Serious protocol deviation by the subject or alteration of the treatment regimen during the trial			
	Death			
	Other			
	Total			

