6.5. Procedure records (FAS)

Table 11 Number of target lesions

Item	Indicator	Experimental group	Control Group	Total
Number of Target Lesions	1 n(%)			
	2 lesions n(%)			
			
	Total (Missing)			
	Statistic			
	P-value			

Note: The number of target lesions is based on the target lesion sites recorded during the use of the test balloon in the procedure. The same applies below.

Table 12 Preprocedure target lesion coronary angiography (by lesion level)

Item	Indicator	Experimental Group	Control Group	Total
Target lesion length (mm)	N(Missing)			
	Mean (SD)			
	Median			
	Q1, Q3			
	Min, Max			
	Statistic			
	P-value			
Reference Vessel Diameter (mm)	N(Missing)			
	Mean (SD)			
	Median			
	Q1, Q3			
	Min, Max			
	Statistic			
	P-value			
Preprocedure target lesion stenosis (%)	N (Missing)			
	Mean (SD)			
	Median			
	Q1, Q3			
	Min, Max			
	Statistic			
	P-value			
Coronary artery lesion type*				
	n(%)			
	n(%)			
	n(%)			
	n(%)			
	Total (Missing)			
	Statistic			
	P-value			
Restenotic Lesion	In-stent restenosis n(%)			
	Drug-eluting balloon restenosis lesions n(%)			
	Other n(%)			
	Total (Missing)			
	Statistical measure			
	P-value			

Item	Indicator	Experimental Group	Control Group	Total
Calcified lesions	None/Mild n(%)			
	Moderate n(%)			
	Severe n(%)			
	None n(%)			
	Total (Missing)			
	Statistic			
	P-value			
Distorted lesions	Yes n(%)			
	No n(%)			
	Total (Missing)			
	Statistic			
	P-value			

*Note: Analysis of lesion types based on core laboratory data: XXX.

Table 13 Non-trial balloon pre-dilatation

Item	Indicator	Experimental group	Control Group	Total
Use of non-trial balloon pre-dilatation*	Yes n(%)			
	No n(%)			
	Total (Missing)			
	Statistical measure			
	P-value			
Number of pre-expansion balloons*	1 n(%)			
	2 n(%)			
	3 n(%)			
	4 n(%)			
	5 n(%)			
	Total (Missing)			
	Statistic			
	P-value			
Diameter (mm)	N(Missing)			
	Mean (SD)			
	Median			
	Q1, Q3			
	Min, Max			
	Statistic			
	P-value			

Item	Indicator	Experimental group	Control Group	Total
Length (mm)	N(Missing)			
	Mean (SD)			
	Median			
	Q1, Q3			
	Min, Max			
	Statistic			
	P-value			
Maximum expansion pressure (atm)	N(Missing)			
	Mean (SD)			
	Median			
	Q1, Q3			
	Min,Max			
	Statistic			
	P-value			
Expansion time (s)	N(Missing)			
	Mean (SD)			
	Median			
	Q1, Q3			
	Min, Max			
	Statistic			
	P-value			

Note: Analyses by device level, except for *use of non-trial balloon pre-dilatation and *number of pre-dilatation balloons at lesion level.

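### The FAS is called intention-to-treat but omits subjects and lesions never attempted with the allocated balloon, and the PPS drops non-completers whose device result is already known

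*Protocol*

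**What the plan says.** **FAS.** Protocol 6.2 and SAP section 3 invoke the intention-to-treat principle. Protocol 6.2 then says the set "refers to the data set constituted by all subjects who participate in the randomized study and receive the investigational product". Protocol 6.3(2) lists non-use of the device after inclusion as a ground for elimination. Neither document says whether receipt or use means opening, inserting or inflating the balloon.

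**Lesion denominator.** The note to SAP Table 11, which it extends to the tables that follow, reads: "The number of target lesions is based on the target lesion sites recorded during the use of the test balloon in the procedure". The primary endpoint is at lesion level, and inclusion criterion (6) allows up to two lesions.

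**PPS.** SAP section 3 defines it as "Subgroup of the completed trial population excluding major protocol deviations (e.g., subjects breaching inclusion or exclusion criteria". The notes to SAP Table 1 count completers as enrolled minus dropouts. Protocol 5.2.3 treats any withdrawal before the end of observation as a dropout, including withdrawal by the investigator after an SAE. SAP Table 3 lists death among the reasons for discontinuation, together with "Serious protocol deviation by the subject or alteration of the treatment regimen during the trial".

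**Missing data.** SAP section 4 imputes undetermined target lesions in the FAS as device failure. It imputes nothing in the PPS.

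**Decision.** SAP 5.4.1 bases the primary test on both sets without saying whether one decides or both must succeed. Protocol 5.1 states that investigators and subjects are not blinded.

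**The concern.** Membership of every set depends on something that happens after an allocation the operator can see. A randomised subject in whom the allocated balloon is never tried, or a second planned lesion that is never tried, leaves no trace in the primary comparison. The failure imputation cannot recover them, because it applies only to target lesions of subjects already in the FAS.

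The PPS has a different fault. Device success is settled when the procedure ends, so a completion-to-discharge rule adds nothing to its assessment and can only discard known results. For procedural success the rule conflicts with the endpoint: Protocol 5.3.1 counts in-hospital death as failure, yet someone who dies in hospital is not a completer and is absent from the PPS analysis of that endpoint.

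Two further texts leave room for judgement. Inclusion criterion (7) refers to a lesion "in which the balloon can be passed through by pre-dilation", while passing the lesion is also part of device success. The Table 3 category on altered treatment could be applied to a change of device. Under Protocol 6.4.4, major deviations are adjudicated by the principal investigators.

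At 96% success only about 2.7 failures per arm are expected (68 x 0.04), so the loss of a few test-arm failures could change a close result.

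**Working it through.** **Inputs.** Success 96% in both arms, margin -10 points, one-sided alpha 0.025, power 80%, 10% dropout (Protocol 6.1.1). The confidence-interval method is left as a placeholder in the note to SAP Table 19, so two common methods are shown. One lesion per subject is assumed.

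**The plan's own figure.** n = 7.85 x (0.96 x 0.04 + 0.96 x 0.04) / 0.10^2 = 7.85 x 0.0768 / 0.01 = 60.3, so 61 per arm. 61 / 0.9 = 67.8, so 68 per arm and 136 in total. This reproduces. The plan thus tolerates 68 - 61 = 7 exclusions per arm against about 2.7 expected failures.

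**Effect of removing one test-arm failure**

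Wald lower limit = d - 1.96 x sqrt[pT(1-pT)/nT + pC(1-pC)/nC], where d = pT - pC.
- 63/68 vs 65/68: d = -0.0294, SE = 0.0403, limit -10.8%. Fails.
- 63/67 vs 65/68: d = -0.0156, SE = 0.0382, limit -9.0%. Passes.

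Newcombe lower limit = d - sqrt[(pT - LT)^2 + (UC - pC)^2], where LT and UC are the Wilson lower limit for the test arm and upper limit for the control arm.
- 64/68 vs 66/68: d = -0.0294, LT = 0.8583, UC = 0.9919, limit -11.5%. Fails.
- 64/67 vs 66/68: d = -0.0154, LT = 0.8764, UC = 0.9919, limit -9.7%. Passes.

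The flip depends on method. By Wald, 64/68 vs 66/68 already passes (-9.8%). By Newcombe, 63/67 vs 65/68 still fails (-10.4%). At the expected 3 failures of 68 in each arm, both pass with nothing removed (Wald -6.9%, Newcombe -8.3%).

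**False-claim rate.** True rates 86% vs 96%, which is the null boundary; 68 per arm; 1,000,000 simulated trials. The share of failures lost is an assumption, because neither document gives one.

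| Failures lost | Newcombe | Wald |
|---|---|---|
| None | 2.2% | 4.2% |
| 10%, test arm only | 3.9% | 7.1% |
| 25%, test arm only | 8.2% | 14.0% |
| 25%, both arms | 5.6% | 10.9% |

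**Which subjects can leave which set**

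| Event after randomisation | FAS | PPS |
|---|---|---|
| Allocated balloon never tried in the subject | Out | Out |
| Planned lesion never tried | Not counted | Not counted |
| Tried; delivery or crossing fails | In, as failure | In, unless classed as a deviation |
| Tried; result undetermined | In, imputed failure | Not imputed |
| Death before discharge, after device use | In | Out |
| Investigator withdrawal after device use | In | Out |

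**The case against.** A reader might infer that device failures and deaths can drop out of both sets. For the FAS the documents do not support that. SAP Table 20 records failed advancement, passage and retraction as results, and undetermined lesions are imputed as failures. A subject who dies after device use remains, and death is not part of device success. What stands for the FAS is the never-attempted subject or lesion, plus the missing definition of use.

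A reader might also take inclusion criterion (7) as a rule that removes lesions the balloon could not cross. It records what the investigator believed at selection. A later failure to cross does not make that belief a violation, and Protocol 6.3(1) asks for a serious one. Likewise, a change of device after balloon failure need not leave the PPS: Protocol 5.5.3 leaves further treatment to the operator, so permitted bailout is not plainly a change of regimen. Both removals are possible under the wording; neither is required.

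It is fair to add that randomisation follows qualifying angiography, so the window for non-use is short and no rate is given. The sets are to be defined before analysis (Protocol 6.2), and a blinded review report precedes database lock (Protocol 8.3). These safeguards limit discretion but do not change the written definitions.

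The strongest objection concerns the remedy. Counting every unattempted lesion as a failure in the primary analysis would penalise both arms for events unrelated to the device. If success fell from 96% to 93% (an assumption), Wald power at 68 per arm would drop from about 85% to 66%. This stands and shapes the fix.

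**Conclusion.** The point holds in a limited form and should be fixed. The intention-to-treat label does not match the FAS as defined, and the lesion denominator has the same gap. The PPS completion rule discards known device results and contradicts the definition of procedural success.

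The numerical effect is confined to results near the margin. It would be too strong to say that losing one or two failures decides the trial, since the expected 3 vs 3 result passes by either method. The error-rate figures rest on assumed loss shares, one lesion per subject and true rates at the null boundary, and they describe whichever set loses the failures. Because attempted failures stay in the FAS, they apply mainly to the PPS, and to the FAS only so far as unattempted lesions would have failed. They matter because the plan does not say that a favourable PPS cannot outweigh an unfavourable FAS.

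**What to change.** - **FAS:** all randomised subjects, in the arm assigned. Record the target lesion site(s) in the EDC before the allocation is shown.
- **Use:** state that any attempt with the study balloon counts as use, and that failed delivery or crossing is a device failure.
- **Unattempted lesions:** pre-specify a sensitivity analysis in which lesions never attempted with the allocated balloon count as failures, and report their number and reasons by arm. SAP section 4 must then say that its failure imputation in the primary analysis covers attempted lesions; otherwise it would take in the unattempted ones as well.
- **PPS:** drop the completion-to-discharge requirement. State that death, SAE withdrawal, failure to cross and device change after a failed attempt are outcomes and not PPS exclusions.
- **Decision rule:** claim non-inferiority only if both FAS and PPS meet the margin.

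The planned 136 subjects need not change. The cost is wording in both documents, one EDC field and some added analysis. The sensitivity result will be slightly less favourable if unattempted lesions occur, and requiring both sets to succeed is a somewhat stricter test.
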